### 6.6.7. Pregnancy Testing

For all female subjects of childbearing potential (FCBP – see Section 6.1.7), a screening serum pregnancy test is required.

A serum or urine pregnancy test (Investigator's discretion) is to be done within 72 hours prior to dosing on Day 1 of every treatment cycle and at the Treatment Discontinuation and Safety Follow-up Visits.

The subject may not receive IP until the Investigator has verified that the result of the pregnancy test is negative.

Guidance for pregnancy testing during screening is provided in Section 6.1.7.

### 6.6.8. Concomitant Medications/Significant Non-drug Therapies/Concomitant Procedures

All prescription, over-the-counter, or herbal medications and therapeutic procedures received from the date of signature of ICF until 28 days after the last dose of subcutaneous azacitidine and 90 days after the last dose of durvalumab (or until the Treatment Discontinuation Visit, whichever period is longer) must be recorded on the appropriate eCRF page. Concomitant medications, therapies, and procedures are those that are received by the subject during their participation in the study as described above. If a medication, therapy, or procedure ended or was stopped prior to the first dose of IP, it will be recorded as a prior medication or as a part of the subject's medical history, as appropriate. See Section 8 for details regarding concomitant medications and procedures.

## 6.7. Efficacy

### 6.7.1. Bone Marrow Aspirate, Biopsy and Peripheral Blood Smear

Samples will be processed as described in the Central Laboratory Manual and submitted for central review along with any pertinent clinical information. Determination of disease status as per the IWG 2006 criteria for MDS and IPSS-R for MDS or Modified IWG 2003 and

cytogenetic risk category as per NCCN guidelines for AML subjects will be done centrally. Results of central review will be utilized for determination of subjects' responses.

During study treatment, bone marrow aspirate (or biopsy if adequate aspirate cannot be obtained) is collected:

- At the end of every 3rd treatment cycle (before starting the next cycle, ideally on Day 22) to confirm suspected disease response or progression, and
- Upon treatment discontinuation.

This bone marrow sample, along with peripheral blood and blood smear slide(s) must be collected at the end of that cycle, but before Day 1 of the next cycle; early enough in order to allow sufficient time to obtain central laboratory results. Samples will be processed according to instructions provided in the Central Laboratory Manual and sent for:

- Central pathology review,
- Central laboratory assessments,
- Central cytogenetics review, and
- CCI

Results from central pathology/cytogenetic review of blood and bone marrow samples will be used for:

- Response assessment,
- General disease status assessment, and
- Monitoring for transformation to AML (only for MDS cohort subjects).

Central laboratory results will be used to programmatically derive the subject's response.

Whenever a bone marrow sample is collected, a peripheral blood sample and peripheral blood smear is to be prepared as well. Specific requirements for submission of bone marrow samples for central review are detailed in the Central Laboratory Manual.

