### Continuation criteria for AML cohort:

- Overall response to treatment: Complete Remission (CR) or Complete Remission with incomplete blood count recovery (CRi) per modified IWG response criteria for AML (Cheson, 2003), or
- Any other clinical benefit including no evidence of progressive disease (PD).

Disease diagnosis for all subjects will be confirmed by the central laboratory prior to randomization, based on blood samples, bone marrow aspirate and biopsy (at screening only).

Bone marrow samples (aspirate and/or biopsy), along with a peripheral blood smear and pertinent clinical information will be submitted for review to an independent pathologist/cytogeneticist to provide consistency for determination of disease classification, assessment, response, and/or progression.

Hematologic parameters including complete blood count (CBC) with white blood cell (WBC) differential and platelets will be assessed by the central laboratory at the frequency described in Section 5 (Table of Events).

CCI [REDACTED]

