#### **7.4. Packaging and Labeling**

The label(s) for IP will include sponsor name, address and telephone number, the protocol number, IP name, dosage form and strength (where applicable), amount of IP per container, lot number, expiry date (where applicable), medication identification/kit number, dosing instructions, storage conditions, and required caution statements and/or regulatory statements as applicable. Additional information may be included on the label as applicable per local regulations.

No blinding is applied in this study.

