## 9.6.1. Primary Efficacy Analysis

### 9.6.1.1. Primary Efficacy Endpoint

The primary efficacy endpoint will be programmatically derived using the results/assessments generated by the central morphologic/cytogenetic and hematology laboratories. This analysis will be conducted after completion of the Stage 1 and Stage 2 portions of the study. A subject is considered evaluable for response if they have undergone the disease status assessment following treatment Cycle 6. Subjects who discontinue from the treatment phase before the first postbaseline efficacy assessment (following treatment Cycle 3) and will be replaced unless the subject had a documented progression of their disease or died will be considered as nonresponders. If one postbaseline disease assessment is performed, this assessment would be considered for response.

The primary efficacy analysis will be based on the ITT population. Analysis based on the EE population will be confirmative and supportive. Test statistics on the difference of proportion of overall response between monotherapy arm and combination therapy arm using unpooled estimate of variance will be used for the primary efficacy endpoint analysis along with confidence intervals.

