For example, the current enrollment (of evaluable subjects) for the MDS disease type is:

	Treatment A	Treatment B
Total Randomized	6	5
Level/Stratum Balance		
Intermediate	4	3
Poor and Very Poor	2	2

The next subject to be randomized has disease type MDS and is Intermediate cytogenetic risk. First step is to calculate the Set of Ranges for the Intermediate level.

If the subject were to be assigned to treatment A the totals would become 5 and 3 and the intermediate level range would be 2, as calculated by Treatment A – Treatment B = 2.

	Treatment A	Treatment B
Intermediate	5	3

If the subject were to be assigned Treatment B the Range would be $4 - 4 = 0$ for the strata.

	Treatment A	Treatment B
Intermediate	4	4

Step 4: Determine the Rank

Continuing with the above example, since Treatment B has the lowest Range, it receives Rank 1 and Rank 2 would be assigned to Treatment A.

Step 5: Determine the Appropriate Cumulative Representation

Using the tables below and considering that in the scenario above, Rank 1 \diamond Rank 2 we would reference Rank Scenario 4 to determine the appropriate Cumulative probabilities. Ultimately based on this Rank Scenario the probability to randomize the patient to treatment A or B will be 1/1 if there is no difference in Rank (Rank Scenario 1 below). Otherwise, the probability will be 9/1 – with the treatment defined as Rank 1 above receiving the higher probability (Rand Scenario 2 below).

Rank Scenario 1: Rank 1 = Rank 2

Rank	Probability	Decimal Probability	Cumulative Probability
Rank 1	1/2	0.5	0.5
Rank 2	1/2	0.5	1.0

Rank Scenario 2: Rank 1 \diamond Rank 2

Rank	Probability	Decimal Probability	Cumulative Probability
Rank 1	9/10	0.9	0.9
Rank 2	1/10	0.1	1.0

Step 6: Query the Random Number table

A table is required that contains a sequence of random numbers between 0.0000 and 1.0000. This list should be uniformly distributed. Based on the next unassigned random number on the list. If the number is \leq Rank 1 cumulative probability, then the treatment in Rank 1 gets the assignment. If the number is $>$ Rank 1 cumulative probability then the treatment in Rank 2 gets the assignment.

Blinding : not applicable for this study.

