10.1. Primary Efficacy Endpoint

The primary efficacy endpoint is the ORR and will be programmatically derived using the results/assessments generated by the central morphologic/cytogenetic and hematology laboratories. In case no central hematology results are available within +/- 8 days of bone marrow samples, local hematology results might be used if available. This analysis will be conducted after completion of the Stage 1 and Stage 2 portions of the study. A subject is considered evaluable for response if they have undergone at least one disease status assessment following treatment Cycle 6. Subjects who discontinue from the treatment phase before the first post baseline efficacy assessment (following treatment Cycle 3) will be replaced unless the subject had a documented progression of their disease or died and will be considered as non-responders. If one post baseline disease assessment is performed, this assessment would be considered for response.

The difference of the proportions for overall response between the azacitidine alone and combination therapy arms will be tested using a standard Wald asymptotic two-sided test with unpooled estimate of variance and presented along with corresponding two-sided 95% CIs.

The hypothesis tested will be:

$$H_0: d = 0$$

versus

$$H_a: d \neq 0,$$

Where $d = p_1 - p_2$ is difference in overall response rate in the combination therapy arm (p_1) versus the overall response rate in the monotherapy arm (p_2).

The test statistic is

$$z = \hat{d}/se(\hat{d})$$

Where, the standard error is computed from the sample proportions as

$$se(\hat{d}) = \sqrt{\frac{\hat{p}_1(1 - \hat{p}_1)}{n_1} + \frac{\hat{p}_2(1 - \hat{p}_2)}{n_2}}$$

Where \hat{p}_1 (respectively \hat{p}_2) is the estimated response rate in the combination therapy arm (respectively monotherapy arm) and is derived as the observed response rates in respective arms.

Myelodysplastic Syndromes Cohort

For the MDS cohort, the primary efficacy endpoint is the proportion of subjects achieving an overall response rate (defined as CR, PR, mCR, and/or HI) as determined using the International Working Group (IWG) 2006 response criteria for MDS ([Appendix 17.2](#)). The ORR will be summarized together with two-sided 95% CI. Subjects discontinued before 6-cycle treatment without achieving overall response will be counted as nonresponders.

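### The protocol does not mask central marrow readers to treatment arm, although the AML response rate turns mainly, and the MDS rate partly, on their blast reading

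*Protocol*

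**What the plan says.** **Source of the endpoint.** SAP 10.1 has overall response rate "programmatically derived using the results/assessments generated by the central morphologic/cytogenetic and hematology laboratories", and Protocol 9.6.1.1 says the same. Protocol 6.7.1 confirms the role of the reading: "Results of central review will be utilized for determination of" subjects' responses.

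**What the reader receives.** Protocol 6.7.1 has samples "submitted for central review along with any pertinent clinical information". The Protocol Summary is similar: marrow samples, "along with a peripheral blood smear and pertinent clinical information will be submitted for review to an independent pathologist/cytogeneticist". Neither place lists or limits the information. Protocol 3.2.2.3 describes the same submission differently, as a smear with biological results. Section 6.7.1 leaves the submission requirements to the Central Laboratory Manual.

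**Who reads.** The Summary calls the reader independent and gives the aim as consistency; Protocol 9.6.1.2 calls the reviewers external.

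**Blinding.** Protocol 7.4: "No blinding is applied in this study". SAP 4.2: "Blinding : not applicable for this study". Nothing in either document withholds the treatment arm from the central reader.

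**The concern.** A marrow blast percentage is a human count, and response is decided by comparing it with a fixed cut. A reader who knows the arm could settle borderline marrows differently in the two arms. Independence from the site does not prevent that, and neither does programming the response category, because the program takes the blast value as given. Protocol 1.5.5 justifies randomization by the internal control it provides, and a difference in reading between arms would weaken exactly that. At stake are the primary comparison in AML and, to a lesser degree, in MDS.

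**Working it through.** **1. Where the blast reading decides response**

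*AML (Protocol Appendix K, SAP 17.3).* CR needs marrow blasts below 5% with neutrophil and platelet recovery. CRi keeps the blast criterion and relaxes the counts. A subject on the wrong side of 5% is neither, whatever the counts; a subject on the right side is nearly always one or the other. The endpoint therefore turns mainly on this one reading.

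*MDS (Protocol Appendix D, SAP 17.2).* The cut is at or below 5%, and response is CR, PR, mCR or HI.
- With recovered counts and a blast fall of at least 50%, crossing 5% only exchanges CR for PR. Both are responses, so the rate does not change.
- HI is a response on blood counts and transfusions alone, with no marrow reading.
- The cut matters mainly for a subject with incomplete counts and no HI, where it separates mCR from stable disease.

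*Cytogenetics.* In the SAP criteria, karyotype enters only cytogenetic CR, which SAP 10.2 treats as a subset of CR. It cannot move the response rate; it matters for the secondary cytogenetic-response endpoint.

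**2. The plan's own sample sizes**

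Unpooled variance, two-sided 5%, 1:1: n per arm = [p1(1−p1) + p2(1−p2)] × (z for alpha + z for power)² / (p1−p2)².
- MDS (72% v 36%, 90% power): 0.432 × (1.960 + 1.282)² / 0.36² = 35.02, so 36 per arm and 72 in total.
- AML (50% v 25%, 80% power): 0.4375 × (1.960 + 0.842)² / 0.25² = 54.9, so 55 per arm and 110 in total.

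Both stated sizes reproduce, and this point disputes neither.

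**3. Illustration of the stakes**

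Test: the SAP 10.1 Wald statistic, z = (observed difference) / √[p̂1(1−p̂1)/n + p̂2(1−p̂2)/n], rejecting when |z| > 1.96. The rejection probability is the exact sum of binomial probabilities over all outcomes that reject. There is no true effect: the control rate is p and the combination-arm rate is p + shift, the shift standing for one-sided misreading. **The shifts are assumptions; the documents give no misreading rate.**

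| Shift | AML (n = 55, p = 25%): extra responders | AML: rejection | MDS (n = 36, p = 36%): extra responders | MDS: rejection |
|---|---|---|---|---|
| 0 | 0 | 5.4% | 0 | 6.2% |
| 3 points | 1.65 | 7.0% | 1.08 | 7.1% |
| 5 points | 2.75 | 9.6% | 1.8 | 8.7% |
| 10 points | 5.5 | 21.8% | 3.6 | 15.7% |

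Extra responders = n × shift. With no shift, rejection exceeds 5% because of the Wald test itself, so the effect of misreading is the rise from the first row. The MDS column is an upper bound: PR and HI stop many borderline blast readings from changing response, so a given rate of misreading produces a smaller shift there.

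**The case against.** **The Central Laboratory Manual may already mask the readers.** Protocol 6.7.1 sends submission requirements there, and it was not available. This stands. The finding is a safeguard that the protocol and SAP do not state, and not proof that readers are unmasked.

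**Pertinent clinical information need not reveal the arm.** A reader might infer that study drug, infusion history or immune-mediated events travel with each sample. The documents do not say so, and Protocol 3.2.2.3 speaks of biological results instead. What stands is that the content is undefined and the two descriptions differ.

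**The blinding statements concern treatment.** One sits with packaging and labeling, the other closes the randomization algorithm. They are best read as describing open-label treatment and do not prohibit reader masking. They also do not provide it.

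**Investigator judgement is already removed.** Independent readers report a value and a program assigns the category. This is a real protection against site bias, but it leaves the reader's value as it is.

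**Blast counts near 5% are imprecise anyway.** One might cite this as evidence of bias. At true blasts of 5%, binomial counting alone gives a reading below 5% in about 45% of 200-cell counts and 47% of 500-cell counts (cell numbers assumed). That is random error, expected in both arms alike. It shows that borderline marrows are uncertain, not that knowledge of arm moves them. The zone is also narrow: at true blasts of 6% a 500-cell count reads below 5% in 15% of samples, and at 7% in 3%.

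**Conclusion.** The point holds as a gap in stated safeguards. The AML primary endpoint depends mainly, and the MDS endpoint partly, on a central blast reading, and neither document masks the reader. Arm-aware reading is possible and is not shown to occur.

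Two stronger readings are not supported. One is that the MDS response rate hinges on the 5% cut as the AML rate does; PR and HI rule that out. The other is that unmasked cytogenetic reading biases response; karyotype does not change the response rate.

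The size is conditional on the assumed shift. In AML, 3 points (between 1 and 2 of 55 subjects) barely matters, at 7.0% against 5.4%. A shift of 10 points (5 to 6 subjects, all misread in one direction) would quadruple the false-positive rate to 21.8%, but nothing in the documents suggests misreading on that scale. This is a worthwhile, inexpensive improvement and not a defect in the sample size or the test.

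**What to change.** 1. In Protocol 6.7.1 and the Central Laboratory Manual, state that post-baseline central morphology is read without knowledge of treatment arm.
2. In the same places, limit the form sent with each sample to subject number, cohort, visit, and transfusion and G-CSF dates, with no arm, infusion or adverse-event data. Bring the descriptions in the Protocol Summary and 3.2.2.3 into line.
3. In SAP 4.2, replace the blinding line with a statement that the study is open-label and that central marrow reviewers are masked to treatment arm.
4. Mask cytogenetic readers in the same way if wanted; this protects the secondary cytogenetic-response endpoint, not the response rate.

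If the manual already masks readers, items 1 and 2 reduce to a cross-reference. The cost is protocol, SAP and manual wording and a requisition form, with no extra reader, visit or procedure. The downside is that sites must use the restricted form.

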### 6.7.2. Cytogenetics

Bone marrow cytogenetic testing is to be completed by the central cytogenetic laboratory whenever a bone marrow aspirate or biopsy is collected for disease assessment. Note: specific handling of the biopsy/aspirate is required in order to be used for cytogenetics testing. See the Central Laboratory Manual for handling instructions.

### 6.7.3. International Working Group Response Assessment

Hematologic response or improvement according to criteria from that of the International Working Group response criteria for MDS (Cheson 2006), and the modified International Working Group response criteria for AML (Cheson 2003) is to be assessed following every 3 treatment cycles prior to Day 1 procedures of subsequent cycles (ie, Cycles 4, 7, 10, etc) and at treatment discontinuation.

Due to the turnaround time required to obtain results from review of bone marrow aspirate and/or biopsy, peripheral blood smear and cytogenetics, IWG response assessment may be done at any time prior to starting the next cycle of treatment. Decisions regarding dose modification and treatment continuation following IWG response assessment may be made based on available local assessments, if necessary, ahead of central hematology and bone marrow pathology assessments becoming available. However, after at least 6 cycles of treatment with IP, if central pathology assessment conveys disease progression, the subject must be notified as soon as possible (not later than the next scheduled study visit) to discontinue further study treatment and to schedule the Treatment Discontinuation Visit, as appropriate.

#### 6.7.4. General Disease Status Assessment

A general assessment of disease status must be performed at the completion of Cycle 6, prior to treatment in Cycle 7, based on available clinical and laboratory assessments.

Subjects who meet any one of the following criteria may continue on to Cycle 7 and beyond, and will have disease status re-assessed prior to beginning each 3rd treatment cycle thereafter based on available clinical and laboratory evaluations and at Treatment Discontinuation Visit. Bone marrow and peripheral blood smear examinations will only be performed after Cycles 3, 6 and every 3rd cycle thereafter, unless additional bone marrow examination is deemed necessary by the Investigator.

For MDS subjects the continuation criteria are:

- Overall response to treatment: CR, mCR, PR as per the IWG criteria for MDS ([Cheson, 2006](#)), or
- Red blood cell transfusion-independence for at least 56 consecutive days, or
- Any HI as per the IWG criteria for MDS ([Cheson, 2006](#)) or
- Any other clinical benefit, including no evidence of progressive disease.

For AML subjects the continuation criteria are:

- Overall response to treatment: CR or CRi as per modified IWG response criteria for AML ([Cheson 2003](#)), or
- Any other clinical benefit, including no evidence of progressive disease.

Subjects who fail to meet one of the above criteria at the end of Cycle 6 will be discontinued from protocol-prescribed therapy and enter the follow-up phase.

Prior to discontinuing a subject, it is recommended that the Investigator contact the sponsor's medical monitor and forward appropriate supporting documents for review and discussion. The decision to discontinue a subject remains the responsibility of the treating physician and will not be delayed or refused by the sponsor.

Confirmation of an RBC-transfusion-independent response/erythroid response (See [Appendix D](#)) requires that the Investigator documents the dates, numbers of units, reason for transfusion, and pretransfusion hemoglobin levels for all RBC transfusions received by the subject throughout the study in the subject's medical record. This will be compared to the subject's RBC transfusion

history over the 56 days prior to randomization, as recorded in the appropriate eCRFs during screening.

#### **6.7.5. Hematology**

Hematology results obtained from the central lab will be used to evaluate response to treatment. In the event that immediate hematology values are needed for clinical decisions, local laboratory results may be used pending the outcome of the central laboratory assessment. However, matching samples must always be sent to the central laboratory and clinical decisions and assessments (such as continuation of treatment beyond Cycle 6) must be reconciled with the results of the central laboratory.

See Section 6.6.6.1 for a list of hematology parameters being assessed by the central laboratory for this study.

#### **6.7.6. Transfusion Assessment**

The following will be recorded for all transfusions the subject received within 56 days (8 weeks) prior to randomization, until 90 days after the last dose of subcutaneous azacitidine or durvalumab or the Treatment Discontinuation Visit, whichever occurs later:

- Type of transfusion (eg, RBC or platelet)
- Number of units
- Reason for transfusion
- Date of transfusion
- Hemoglobin value for which any RBC transfusion is given
- Platelet value for which any platelet transfusion is given.

Red blood cell transfusions administered for surgical procedures, significant hemorrhagic events, or other reasons documented as unrelated to MDS-associated anemia will not be counted in the assessment of baseline RBC transfusion requirements, efficacy, or progressive disease status.

Red blood cell transfusion-independent response or improvement will be assessed according to criteria from that of the IWG criteria for MDS (Cheson 2006) (Appendix D).

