7.2. Baseline Characteristics

Baseline clinical characteristics include temperature (°C), systolic blood pressure (SBP, mmHg), diastolic blood pressure (DBP, mmHg), pulse (bpm), respiratory rate, Eastern Cooperative Oncology Group (ECOG) performance status (PS) and baseline electrocardiograms (ECGs) will be summarized.

Coagulation test performed at screening will be summarized. Overall interpretation from coagulation test will be summarized along with prothrombin time/international normalized ratio, activated partial thromboplastin time, and thrombin time.

Baseline laboratory assessments from central laboratory will be summarized for Hgb, platelet count, absolute neutrophil count (ANC), white blood cell (WBC) count, creatinine, aspartate aminotransferase (AST/SGOT), alanine aminotransferase (ALT/SGPT) and total bilirubin.

Creatinine clearance (CrCl) will be assessed at screening by the central laboratory. Creatinine clearance is estimated using the Cockcroft-Gault formula where $CrCl(mL/min) = (140 - \text{age}) (\text{weight [kg]}) / 72 (\text{serum creatinine [mg/dL]})$; for females, the formula is multiplied by 0.85 (Cockcroft, 1976). The CrCl will be summarized as continuous variable. The creatinine clearance will be normalized to an average surface area (size) of 1.73m². The corrected CrCl will be summarized as continuous variable and category variable defined as chronic kidney disease (CKD) stages (Stage 1, 90+; Stage 2, 60-89; Stage 3, 30-59; Stage 4, 15-29; Stage 5, <15).

Cytogenetic risk classifications ([Appendix 17.4](#) and [17.5](#)) will be summarized with frequency counts and percentages. For MDS cohort, IPSS-R will be summarized along with hemoglobin, platelet and absolute neutrophil count used in the derivation. Bone marrow blast will be summarized as continuous variable and category variable as defined in IPSS-R ($\leq 2\%$; $> 2\% - < 5\%$; $\geq 5\% - \leq 10\%$; $>10\%$).

Baseline RBC transfusion burden and platelet transfusion burden will be summarized. The baseline transfusion burden is defined the total number of units of transfusion received before or on the first dose date. Only RBC transfusions given for hemoglobin of ≤ 9.0 g/dL before or on the first dose date will count in the baseline RBC transfusion burden.

The time from initial diagnosis to randomization will also be summarized.

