15. CHANGES TO THE STATISTICAL ANALYSES SECTION OF THE PROTOCOL

Response derivations have been updated for consistency with IWG Response Criteria in Myelodysplasia (Cheson, 2006) and Modified IWG AML Response Criteria (Cheson, 2003).

IA requirements and definition of EE population have been detailed in order to specify that subjects assigned to Arm A, who received less than 3 cycles of durvalumab and continued under azacitidine monotherapy are to be excluded from interim analysis and/or in the EE population.

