Erythroid response (HI-E) (Pretreatment < 11 g/dL)	
 ▪ Hgb increase by \geq 1.5 g/dL in \geq 8 weeks 
OR
 
 ▪ Relevant reduction of units of RBC transfusions by an absolute number of at least 4 RBC transfusions/8 weeks compared with the pretreatment transfusion number in the previous 8 weeks. Only RBC transfusions given for a Hgb of \leq 9.0 g/dL pretreatment will count in the RBC transfusion evaluation 
 ▪ For Hgb, 7/3 rule should be applied first
Platelet response (HI-P) (Pretreatment < $100 \times 10^9/L$)	
 ▪ in \geq 8 weeks Absolute increase of $\geq 30 \times 10^9/L$ for patients starting with $> 20 \times 10^9/L$ 
OR
 
 ▪ Increase from $\leq 20 \times 10^9/L$ to $> 20 \times 10^9/L$ and by at least 100%

Neutrophil response (HI-N) (Pretreatment $< 1.0 \times 10^9/L$)	
 ▪ in ≥ 8 weeks At least 100% increase and an absolute increase from mean of pre-dose of $> 0.5 \times 10^9/L$
---	---

AML = acute myeloid leukemia; Hgb = hemoglobin; RBC = red blood cell

Source: Cheson BD, Greenberg PL, Bennett JM, Löwenberg B, Wijermans PW, Nimer SD, et al. Clinical application and proposal for modification of the International Working Group (IWG) response criteria in myelodysplasia. Blood. 2006; 108(2): 419-25.

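### The SAP's HI-E transfusion rule leaves out the protocol's exclusion of RBC transfusions given for bleeding, surgery or other non-MDS reasons, so some subjects could count as MDS primary-endpoint responders under the SAP but not by that rule under the protocol

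*Protocol*

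**What the plan says.** **Protocol 6.7.6 (Transfusion Assessment).** "Red blood cell transfusions administered for surgical procedures, significant hemorrhagic events, or other reasons documented as unrelated to MDS-associated anemia will not be counted", and the sentence continues "in the assessment of baseline RBC transfusion requirements, efficacy, or progressive disease status". The same section lists "Reason for transfusion" among the items recorded for every transfusion, from 56 days before randomization. Section 6.7.4 requires the reason to be documented to confirm an erythroid response and sets the comparison period as the 56 days before randomization.

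**Protocol Appendix D.** The HI-E entry counts only RBC transfusions given at a hemoglobin of 9.0 g/dL or less. Section 6.7.6 refers to this appendix immediately after stating the reason exclusion.

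**SAP Appendix 17.2.** HI-E requires pretreatment hemoglobin below 11 g/dL and either a hemoglobin rise of at least 1.5 g/dL or a fall in RBC units "by an absolute number of at least 4 RBC transfusions/8 weeks compared with the pretreatment transfusion number in the previous 8 weeks". The only limit on which transfusions count is the 9.0 g/dL threshold. In the same appendix, any RBC or platelet transfusion after CR or PR counts as relapse, and transfusion dependence is one of the items in the PD definition.

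**SAP 7.2.** "The baseline transfusion burden is defined the total number of units of transfusion received before or on the first dose date", with the same hemoglobin filter for RBC units and no time window.

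**SAP 10.1.** For MDS, "the primary efficacy endpoint is the proportion of subjects achieving an overall response rate (defined as CR, PR, mCR, and/or HI"), derived by program.

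**SAP 15.** "Response derivations have been updated for consistency with IWG Response Criteria in Myelodysplasia". The section does not mention the reason exclusion.

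**The concern.** The protocol has two filters for RBC transfusions in efficacy: the reason for the transfusion and the hemoglobin at which it was given. The SAP carries over only the second. Appendix 17.2 is the detailed specification for a programmed primary endpoint, so a programmer working from it would count units given for a bleed or an operation.

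Two errors become possible. A subject transfused for a bleed before treatment, who does not bleed again, can show a large enough fall in units to meet HI-E without any change in MDS-related transfusion need. In the other direction, on-study units given for bleeding or surgery can offset a real reduction and hide a transfusion-limb HI-E.

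Because HI alone is a response, either error can change a subject's primary outcome in the MDS cohort. False responders can arise only among true non-responders. If the affected share is the same in both arms, they raise the lower response rate more and shrink the difference. The same HI rule serves the AML secondary endpoint of hematologic improvement.

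**Working it through.** **1. The same subject under each rule.** Take pretreatment hemoglobin below 11 g/dL; 4 RBC units for a bleed, each at hemoglobin 9.0 g/dL or less, in the 8 weeks before treatment; and no units in an on-study 8-week period.

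- SAP 17.2: 4 − 0 = 4, which meets the threshold of 4. The subject is HI-E and an ORR responder.
- Protocol 6.7.6 with Appendix D: the 4 units are dropped, so 0 − 0 = 0. There is no HI-E by the transfusion limb.

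**2. The reverse case.** Take 4 MDS-related units before treatment and, on study, none for MDS anemia but 1 for a bleed at hemoglobin 9.0 g/dL or less.

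- SAP 17.2: 4 − 1 = 3, below the threshold.
- Protocol: 4 − 0 = 4, HI-E.

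The subject loses responder status only if no other 8-week period, no hemoglobin rise, and no HI-P, HI-N, CR, PR or mCR qualifies.

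**3. The planned MDS sample size.** Inputs (protocol 9.3.1, SAP 4.3.1 and 10.1): 36% v 72%, 72 subjects allocated 1:1, 5% level, 90% power, two-sided Wald test with unpooled variance.

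n per arm = (1.960 + 1.282)² × (0.36 × 0.64 + 0.72 × 0.28) / 0.36² = 10.51 × 0.432 / 0.1296 = 35.02, rounded up to 36, or 72 in total. This reproduces the plan. With 36 per arm the SE is √(0.432/36) = 0.1095, and power is Φ(0.36/0.1095 − 1.96) = 90.8%.

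**4. Size of the effect.** One subject is 1/36 = 2.8 points of an arm's ORR.

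The documents do not say how often subjects enter with at least 4 bleeding or surgical units. Let s be that share, assumed equal in both arms, and let every true non-responder among them convert. Then p′ = p + s(1 − p), and the difference becomes 0.36(1 − s). Expected false responders per arm are 36 × s × (1 − p).

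| Assumed s | Control ORR | Combination ORR | Difference (points) | False responders, control / combination | Power |
|---|---|---|---|---|---|
| 0 | 36.0% | 72.0% | 36.0 | 0 / 0 | 90.8% |
| 2% | 37.3% | 72.6% | 35.3 | 0.46 / 0.20 | 89.6% |
| 5% | 39.2% | 73.4% | 34.2 | 1.15 / 0.50 | 87.6% |
| 8% | 41.1% | 74.2% | 33.1 | 1.84 / 0.81 | 85.5% |

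Full conversion makes each row an upper bound on the loss from false responders at that s. Hidden responders are not in the table. If the arms differed in either error, the difference could move in either direction.

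**The case against.** The strongest reply is that there is no conflict, only silence. The 9.0 g/dL wording in SAP 17.2 is the protocol's own Appendix D wording, and in the protocol it stands together with 6.7.6: drop the non-MDS units, then apply the hemoglobin threshold. Repeating the appendix repeals nothing. SAP 5.3.4 also mentions a derived data set specification that is not among these documents and that could contain the filter.

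Part of this stands. A reader might infer that the SAP reverses the protocol rule, but the documents do not support that: the SAP omits the exclusion and does not contradict it. The omission still matters. SAP 17.2 says which transfusions count and gives only one of the two criteria, and SAP 15 reports that response derivations were updated without mentioning the other.

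Other stronger readings also fail:

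- *Any resolved pre-study bleed makes a responder.* All the conditions in step 1 must hold, including at least 4 fewer units in an on-study 8-week period. Protocol 7.2.2.1 associates azacitidine with anemia, particularly in the first 2 cycles.
- *On-study bleeding units cancel HI-E.* They can hide the transfusion limb, but other limbs and other periods remain open.
- *SAP 7.2 affects the primary endpoint.* It is a descriptive baseline summary. HI-E uses its own pretreatment count.
- *A transfusion for bleeding can by itself cause PD.* As printed, SAP 17.2 requires a blast increase as well, and the transfusion item applies only to subjects who were transfusion-independent at baseline.
- *A loss of power has been shown.* Both the shares and the full conversion are assumptions.

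**Conclusion.** The point holds in a limited, conditional form. The protocol excludes RBC transfusions by reason from efficacy. The SAP's HI-E derivation does not carry that exclusion, and SAP 15 does not disclose the omission. Followed as written, the SAP can classify a subject as an MDS primary-endpoint responder whom the protocol would not count by the transfusion limb, and it can hide a transfusion-limb HI-E.

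Each misclassified subject moves an arm's ORR by 2.8 points. On assumed shares of 2%, 5% and 8%, the loss of power through false responders is at most from 91% to 90%, 88% and 86%. Those figures assume equal shares in both arms, full conversion of affected non-responders, 36 subjects per arm and the planned rates. The rule mismatch itself rests on no assumption. Whether it reaches the reported ORR depends on how the derivation was programmed, which the documents do not show.

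**What to change.** In SAP 17.2, state that RBC transfusions whose recorded reason is surgery, significant hemorrhage or another documented cause unrelated to MDS anemia are removed before the hemoglobin filter is applied. Do this in the HI-E transfusion limb for units both before and after treatment start. Apply the same exclusion to RBC transfusions in the relapse-after-CR/PR rule and in the transfusion-dependence item of PD.

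For consistency, apply it to the descriptive RBC burden in SAP 7.2. Take the pretreatment count over the 56 days before randomization, as in protocol 6.7.4.

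Alternatively, if the sponsor wants the hemoglobin filter alone, list that departure from protocol 6.7.6 in SAP 15 and add a sensitivity analysis of ORR with the exclusion applied.

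The cost is one programming filter on a field that is already collected. The sample size stays at 72, and the reported ORR may change slightly.
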